Response to these alerts might be escalated (e.g., calling emergency contact or wellness check) as clinically indicated. The response provided by our risk monitoring team and/or the treating clinician will include a list of local resources, including information about crisis hotlines.

If a participant is determined to be not eligible because they need a higher level of care, either at screening or over the course of the study, resources will be provided to the

individual, including a list of treatment resources in the area. If a participant is determined to need continued care after the end of the 12-week treatment intervention, a list of treatment resources will be shared with the participant.

The consent form will advise participants that staff will monitor any alerts triggered by responses to symptom surveys. We include the following in the consent form: *"We will ask you questions about potentially sensitive topics. If your responses to study surveys at any point indicate that you are feeling suicidal and with a plan to harm yourself or you endorse thoughts of harming your infant or having harmed your infant, our clinical team will be notified and will review this information, confidentially. The clinical team will contact you to determine if there are safety concerns that require immediate help, may follow-up on potentially concerning responses to the symptom surveys, and may provide referrals to clinical services that may be available to you. If we are concerned that you are going to seriously harm or kill yourself or someone else imminently, we may need to share that information with someone outside of our research team to ensure your safety or the safety of others. We may additionally need to share information with your current provider."*

The consent form also includes the following section on mandated reporting: *"Identifying information may be released in some circumstances. Specifically, the study staff are legally required to report known or reasonable suspicion of abuse to a child, elder, or dependent adult and serious threats against a reasonable identifiable victim or victims. Information will be released only to responsible agencies and others that the study staff are mandated to report to by law or University policy, including relevant authorities such as law enforcement. We also might need to release information about you if you are in danger and need emergency care (for example if we believe there is an imminent threat of suicide or serious self-harm or that you may harm others). Any relevant information obtained during the course of the study can be used in mandated reporting if indicated (e.g., emergency contact). This information obtained may be shared with your treating OBGYN provider and your clinical team. You have the right to privacy, and it is your choice whether or not you answer a question or provide information."*

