Study Title: HARMONY - Health And Response: Digital Markers for Outcomes in Perinatal Depression Treatment Study
Lay title: HARMONY Study

Protocol version: 12/5/2025

Principal Investigator:

[name]
University of California, Los Angeles
[name]
[name]
[name]

Overview: The purpose of this study is to determine if the addition of digital sensing data collected from phones and watches during the early stages of perinatal depression (PND) treatment can better predict treatment outcomes than using self-reported symptoms alone. The overarching goal is to develop a tool to predict the right treatment at the right time for individuals with PND, enhancing clinical decision making and ultimately improving the scalability and accessibility of historically inaccessible PND treatments.

STAND for PND: The UCLA Depression Grand Challenge (DGC) has previously developed a technology-assisted, scalable therapy system called STAND (Screening and Treatment for ANxiety and Depression) for perinatal depression (PND) and has demonstrated in an initial randomized clinical trial that this treatment intervention to be as effective as psychiatrist delivered care for PND. In this study, we will administer STAND for PND for up to 12 weeks as part of study participation. There will be no comparison between our treatment intervention and a treatment as usual condition, as this is not a trial of efficacy. In the STAND for PND treatment model, women with moderate symptoms will be routed to coach-guided, digital cognitive behavioral therapy (CBT) tailored to PND, which has been demonstrated to be an effective treatment approach for PND (e.g., Heller et al., 2019; Pettman et al., 2023; Loughnan et al., 2019). Women with severe depression or suicidality will be routed to clinician delivered CBT, with CBT demonstrated to be an effective treatment approach for PND (e.g., Nillni et al., 2018; Cuijpers et al., 2023; Frieder et al., 2019). Women receiving CBT tailored for PND may be referred to a UCLA clinic for pharmacotherapy if recommended by the clinical team. Symptoms will be regularly monitored in all participants throughout the intervention period.

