Sample: We aim to enroll women who are in their last trimester of pregnancy (28 weeks' gestation) through postpartum period (12 weeks after delivery) and are experiencing moderate-to-severe depression. We estimate needing to enroll 250 women in order to obtain complete data on 200 women. Women will be recruited from participating UCLA Health clinics in the Los Angeles area.

Inclusion Criteria:

- At least 18 years of age
- Able to read and communicate in English
- Between 28 weeks pregnant and 12 weeks postpartum
- Moderate-to-severe depression, as defined by Edinburgh Postnatal Depression Scale (EPDS) score ≥ 11
- Not currently seeing a provider for mental health care
- Own functioning iOS smartphone (iPhone 11 or newer, iOS 18 or newer) with access to reliable data plan and Wifi)
- Able to read and understand a written informed consent form
- Willingness to participate in treatment through the study and follow all study procedures, including providing HIPAA Authorization for research, installing a study app on personal iPhone, and wearing the provided Apple Watch for at least 20 hours every day in the first four weeks of the study (including while sleeping)

Exclusion Criteria:

- Currently receiving treatment by a therapist or a psychiatrist
- Unstable suicidality (e.g., 2 or more suicide attempts or self-injurious behaviors resulting in hospitalization in the last 6 months)
- Current substance use disorder that interferes with treatment: specifically, patients meeting diagnostic criteria for Substance Use Disorder (SUD) will be eligible for inclusion only if they are able to attend sessions while not under the influence of that substance, with the exception of individuals abusing opiates or freebase cocaine, who will be excluded
- Principal diagnosis of psychosis unrelated to depression (unipolar or bipolar)
- Neurological conditions
- Severe uncontrolled medical conditions (e.g., anorexia nervosa, cardiac conditions requiring continuous monitoring)
- Cognitive impairment (e.g., developmental disability, dementia)
- Previously participated in the UCLA Depression Grand Challenge "New Moms Mood Tracking & Wellbeing Study" (IRB #20-001924)

Study Procedure:

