- After the first treatment session and at the end of clinical care, participants will also be sent a link to complete an assessment of their clinical care (Care Evaluation and/or Treatment Satisfaction). This survey takes less than 5 minutes to complete.

Treatment Intervention: Participants will be assigned to one of the following STAND for PND treatment conditions depending on their screening depression symptom severity scores. The STAND for PND treatment intervention provides access to a system of care, in which type of treatment is allocated based on presenting depression symptomatology. Any endorsement of suicidality with intent or means, regardless of depression inventory score, is considered appropriate for STAND Clinical Care (Tier 3). Participants will be notified of their treatment assignment at the time of enrollment.

The remote onboarding session, which includes installation of the study app on the participant's iPhone, must occur prior to the initiation of care. An Orientation or Intake session for participants assigned to Tiers 2 and 3, respectively, will occur prior to treatment initiation. As such, at least one week of digital sensing data collection will occur between baseline and initiation of treatment.

Tier 2 - PND Digital Therapy with Coaching: Participants with a recent EPDS score in the moderate range (11-18) and no current suicidality will be given access to a perinatal depression online cognitive-behavioral therapy course, which is called the ParentMood program. Some of the lesson content is presented in the form of illustrated videos. Following each lesson, participants can download a document that summarizes the key information in each lesson, and which includes practical homework exercises that reinforce the content of the lesson. Participants are encouraged to practice their lesson homework for at least one week before starting the next lesson. Lessons will be completed sequentially. The ParentMood program can be accessed through the study app that participants will be guided to install on their iPhone during the onboarding session. Participants additionally have the option of accessing the content through a web-browser. Participants may receive up to 9 coaching sessions with their assigned Coach, in addition to an initial Orientation session, which will occur through secure video conference. While the initial Orientation session is required for study participation, the additional coaching sessions thereafter are optional.

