All coaching sessions will be recorded for supervision purposes. Recordings will be stored in a HIPAA compliant cloud-based storage solution, where access is restricted to study team members listed on the IRB. Participants are informed about the requirement to record coaching sessions in the consent form.

Participants have the option of allowing these recordings to be retained and used for future research when providing consent; if a participant does not opt-in to sharing these recordings for research purposes, they will be deleted once their participation in the study has ended.

Tier 3 – Clinical Care: Participants with a recent EPDS score in the severe range (19-30) and/or significant suicidality with intent or means will be given access to a clinical care, which entails weekly psychotherapy sessions. The number and schedule of psychotherapy sessions in the study is determined by the clinical care team.

Treatment appointments will occur through secure video conference. All treatment sessions, including the intake session, will be recorded for supervision purposes. Recordings will be stored in a HIPAA compliant cloud-based storage solution, where access is restricted to study team members listed on the IRB. Participants are informed about the requirement to record treatment sessions in the consent form. Participants have the option of allowing these recordings to be retained and used for future research when providing consent; if a participant does not opt-in to sharing these recordings for research purposes, they will be deleted once their participation in the study has ended.

If the clinical team believes that consultation with a psychiatrist is warranted, a referral will be made to a UCLA Health clinic (e.g., the MOMS Clinic) for a consultation session and possible pharmacotherapy.

Treatment Changes: Treatment changes (between Tiers 2 and 3) will be made according to the following criteria:

- If any participant endorses suicidality with intent or means, treating clinicians will be notified, and the participant will be offered Tier 3 Clinical Care if they are not already actively engaged in Tier 3 care.
- Tier 2 Digital Therapy participants may be offered Tier 3 Clinical Care in the case that their EPDS depression scores are in the severe range for two consecutive assessments.

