- Tier 3 Clinical Care participants who have completed their course of therapy may be offered additional therapy sessions within the 12-week study duration in the case that their EPDS depression scores are in the severe range for two consecutive assessments.
- Tier 3 Clinical Care participants who have completed their course of therapy may be offered Coaching and given access to the digital therapy program if their EPDS depression scores are in moderate range (11 or higher) on weekly EPDS assessments after completing therapy.
- Participants who miss over four appointments (not due to clinician/coach cancellation or schedule changes) may be discontinued from treatment.
- If upon completion of all available clinical appointments, a participant requires additional care, they would be referred to appropriate resources in the community.

Both treatment interventions provide evidence-based care. Tier 3 Clinical Care will be provided by a Licensed Clinical Social Worker ([name] or [name]).

Participants will not be billed for treatment provided in Tier 2, or for psychotherapy provided in Tier 3. If participants are referred to a UCLA Health Clinic for a consultation with psychiatry, the scheduling and billing will be managed by the clinic and is not part of our research workflows. The cost to see a psychiatrist and receive medication will depend on the participant's prescription coverage and co-payment plan.

Study End: Participants will receive information by email about their progress in the study and compensation earned. They will also receive instructions for withdrawing from the study configuration in the study app and instructions to delete the study app from their iPhone, if preferred. For participants who drop from the study early, or who do not provide enough data to meet the threshold to be able to keep the Apple Watch, they will be provided instructions for unpairing and resetting the watch, and will be sent shipping materials to be able to return the Apple Watch if it was provided to them to our research offices.

Time Commitment: The total time expected for study participants is 270 minutes (approximately 4.5 hours). This estimate is based on the time required to complete the following:

- Online screening & enrollment: 20 minutes (not included in compensation)
- Baseline self-report surveys (60 minutes)
- Onboarding session (60 minutes)
- Weekly depression symptom ratings (65 minutes; 5 minutes each for 13 weeks)

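### The initial tier rules assign no tier to an eligible woman with EPDS 11-18 and suicidality without intent or means, while the overview sends her to clinician care

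*Protocol*

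**What the plan says.** Four places in the Protocol bear on who receives which treatment at the start.

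- **Inclusion and Exclusion Criteria.** Entry requires "Moderate-to-severe depression, as defined by Edinburgh Postnatal Depression Scale (EPDS) score ≥ 11". On suicidality, the exclusion is limited to the unstable kind: "Unstable suicidality (e.g., 2 or more suicide attempts or self-injurious behaviors resulting in hospitalization in the last 6 months"). Suicidal thoughts without intent or means do not exclude a woman.
- **Treatment Intervention, general paragraph and Tier 2.** The general paragraph states: "Any endorsement of suicidality with intent or means, regardless of depression inventory score, is considered appropriate for STAND Clinical Care (Tier 3"). The Tier 2 rule then says: "Participants with a recent EPDS score in the moderate range (11-18) and no current suicidality will be given access". Its suicidality condition does not mention intent or means.
- **Treatment Intervention, Tier 3.** Weekly psychotherapy is reserved for this group: "Participants with a recent EPDS score in the severe range (19-30) and/or significant suicidality with intent or means".
- **STAND for PND overview.** "Women with severe depression or suicidality will be routed to clinician delivered CBT". Here suicidality carries no qualifier. The preceding sentence sends women with moderate symptoms to coach-guided digital CBT.

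Treatment Changes also uses an EPDS range, for women who have finished Tier 3 therapy: "EPDS depression scores are in moderate range (11 or higher) on weekly EPDS assessments after completing therapy". Tier 2 gives the moderate range as 11-18.

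**The concern.** The two tier rules use different thresholds for suicidality. Tier 2 is closed by any current suicidality. Tier 3 is opened, for a woman scoring below 19, only by suicidality with intent or means. Between the two lies an eligible group with no assigned treatment: EPDS 11-18 with suicidal thoughts but neither intent nor means. The overview does place this group, in clinician-delivered care, so the protocol contradicts itself as well as leaving a gap.

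The treatments differ in substance. In Tier 2 the coaching sessions after Orientation are optional, whereas Tier 3 consists of weekly psychotherapy. Women are told their tier when they enrol, and the protocol describes no adjudication step for a case that fits neither rule. What such a woman receives would therefore depend on which passage the staff member, or whoever programmed the assignment, had followed.

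**Working it through.** No sample size, power or error rate is involved, and the plan states no figure to reproduce. The check is a complete enumeration of the written rules.

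**Inputs**
- EPDS range among eligible women: 11 (Inclusion Criteria) to 30 (upper end of the Tier 3 range), so 30 − 11 + 1 = 20 scores. Of these, 8 lie in 11-18 and 12 in 19-30.
- Suicidality states that the rules distinguish: none; present without intent or means; present with intent or means.
- Combinations: 20 × 3 = 60.

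**Rules as written**
- Tier 2 if EPDS is 11-18 AND suicidality is none.
- Tier 3 if EPDS is 19-30 OR suicidality is with intent or means.
- Overview: clinician-delivered CBT if EPDS is severe OR any suicidality is present; otherwise digital CBT.

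| EPDS | Suicidality | Combinations | Tier rules | Overview |
|---|---|---|---|---|
| 11-18 | none | 8 | Tier 2 | digital |
| 11-18 | without intent or means | 8 | **neither** | **clinician** |
| 11-18 | with intent or means | 8 | Tier 3 | clinician |
| 19-30 | none | 12 | Tier 3 | clinician |
| 19-30 | without intent or means | 12 | Tier 3 | clinician |
| 19-30 | with intent or means | 12 | Tier 3 | clinician |

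**Result.** Exactly one tier: 8 + 8 + 12 + 12 + 12 = 52. Both tiers: 0. Neither tier: 60 − 52 = 8. The overview and the tier rules agree in all 52 assigned combinations and part only in the remaining 8.

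**Two ways to close the gap from the existing text, with opposite results**
- If the overview governs, the 8 combinations join Tier 3: Tier 2 has 8 and Tier 3 has 44 + 8 = 52.
- If the Tier 2 condition was meant as shorthand for no suicidality with intent or means, they join Tier 2: Tier 2 has 8 + 8 = 16 and Tier 3 has 44.

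**Does another section settle it?** The suicidality trigger in Treatment Changes again requires intent or means; its other criteria turn on EPDS scores, missed appointments or completed care. Follow-up at Prescreening is likewise worded for intent or means. The Risk Protocol responds to any suicidal thoughts with an automated alert, outreach by a contracted 24/7 crisis service and review by the study's risk team, but it assigns no tier.

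**The case against.** The strongest reply is that this is one missing qualifier. The overview is narrative, and its own moderate-symptoms clause could be read to cover these women. The operative statements in Treatment Intervention, Tier 3 and Treatment Changes all speak of intent or means, so the Tier 2 wording may be shorthand for the same thing. That is plausible, but the protocol does not say it, and the overview's explicit suicidality clause points the other way. The gap stands on the text.

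Other parts of the reply do limit the point, because a reader might infer more than the documents support.

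- **That these women are left unmonitored.** They are not. The Risk Protocol's alerts and outreach do not depend on tier, depression and suicidality are asked about weekly, and any participant who later endorses intent or means is to be offered Tier 3.
- **That the prediction analysis is biased.** The study asks whether sensing data added to self-report predict outcome better than self-report alone, within one treated cohort and with no comparison against usual care. Tier settles which treatment is given, but no route is shown from inconsistent tiering of a subgroup to bias in that comparison. The analysis plan is held in another document.
- **That Treatment Changes contradicts itself.** A Tier 3 completer with severe scores on two consecutive assessments can satisfy both the further-therapy and the coaching provisions. Both are discretionary offers with different triggers, and nothing makes them mutually exclusive. Only the label is loose: 11 or higher reads as a floor, whereas Tier 2 ends the moderate range at 18.
- **That a given number of women is affected.** The protocol offers no rate from which to derive one.

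**Conclusion.** The point holds for initial allocation. Followed literally, the rules give no tier in 8 of 60 combinations of score and suicidality state, all of them EPDS 11-18 with suicidality without intent or means, and the overview routes those same 8 to clinician care. The 8 of 60 counts combinations, not women. The documents do not allow the group to be sized; for scale only, each 1% of the 250 planned enrolments would be 2.5 women. The conclusion does not depend on that share.

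It rests on two readings: that the Tier 2 condition means what it says, and that suicidality without intent or means falls outside the unstable-suicidality exclusion, whose examples are attempts or self-injury leading to hospitalization. The correction is needed because the treatment of an at-risk group is undefined in one place and defined in another. Existing risk monitoring reduces the immediate danger but does not supply the missing assignment. The differing label for the moderate range is a secondary wording matter.

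**What to change.** Reconcile the STAND for PND overview, the general paragraph and Tier 2 rule under Treatment Intervention, and the Tier 3 rule, so that every eligible combination of EPDS score and suicidality response maps to exactly one initial tier. Use one defined suicidality term throughout; a six-row table like the one above would be enough. The clinical leads decide which tier applies to the unassigned group. Then check the allocation logic, in REDCap or wherever the assignment is made, against the agreed table.

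In Treatment Changes, align the label of the moderate range with the 11-18 used for Tier 2, and leave the discretionary offers as they are.

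The cost is a wording amendment and a logic check, with no additional participants, assessments or procedures.

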messages through the myChart patient portal. If they patient indicates an interest via the myChart message, a member of the ECRI team or the study team will respond with information about the study webpage. The recruitment messages will include a link to our study webpage, as well as study team contact information. We will also work with UCLA CareConnect teams to deploy custom smartphrases, such that information about the study can be shared in a patient's after-visit summary if the smartphrase is entered in CareConnect during a clinical encounter.

Recruitment partners include providers and clinic staff at UCLA Health OB/GYN Clinics, the UCLA West Medical Clinic, Inpatient and Outpatient Social Workers, Lactation Consultants, and the MOMS Clinic.

Additional recruitment strategies may be deployed by the study team, including posting IRB-approved recruitment materials in social media channels, sharing with community organizations, and contacting other channels for distribution (e.g., postpartum support groups).

Prescreening: Prospective participants will be directed to our study webpage. Interested prospective participants can proceed with completing prescreening questions online, which includes self-reporting on demographics, eligibility screening items, and completing an online self-report assessment of current depression symptom severity. Interested prospective participants can speak with a member of the study staff or consult online FAQ before proceeding with online eligibility screening. As stated in the eligibility criteria, eligible participants must have a recorded EPDS score of 11 or higher within the previous 7 days in order to be enrolled in the study. If there are delays in obtaining consent and completing enrollment, an EPDS may need to be re-administered to ensure eligibility and tier assignment.

Women will be notified immediately about whether they are eligible to participate in the study; if additional information is needed to determine eligibility (e.g., confirm exclusionary diagnosis), information will be provided to the prospective participant about next steps and expected timeline.

Women who endorse suicidality with intent or means as part of online screening will receive follow-up for risk assessment, as outlined in our Risk Protocol.

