All parts of the baseline must be completed before the first payment is issued, including baseline surveys and the remote onboarding session. Subsequent compensation will be provided at the end of each approximately four-week period (i.e., after block 1, 2 and 3), once study assessments are completed and any outstanding data missingness issues have been resolved. Participants who discontinue study participation before the end of a given four-week interval will not receive compensation based on amount of tasks completed in that four-week interval.

Study staff will remind participants to use the funds within 365 days of being added to the card to avoid incurring any fees beyond that time. If a participant does not want to receive compensation through a prepaid Visa debit card, they can ask study staff for eGift Cards instead, which will be ordered and mailed at these same intervals. Participants will be notified of the estimated time to receive alternative eGift Cards.

Risk Protocol:

As this study is minimal risk, no independent Data Safety Monitoring Board or Committee is instituted for this study. If it is determined in the future that such a committee or board is necessary, we will implement one.

Below, we share information regarding our Risk Protocol, which is developed by the study team and overseen by study PIs, Drs. [name] and [name]. Our Risk Protocol Supervisors are our staff social workers, [name] and [name]. Staff members who have direct contact with participants and may conduct a follow-up assessment following endorsement of suicidality or harm to infant are trained and supervised by these Risk Protocol Supervisors. We contract a crisis call center to

make initial outreach following endorsements of suicidality in remote surveys. All documentation is maintained in our REDCap database.

A Risk Protocol is necessary for this study, as women experiencing moderate-to-severe depression will be asked to frequently report on their symptoms of depression, including suicidality, over the course of the study. The following protocol will be implemented in response to reports of suicidal ideation or worsening depression.

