In response to an endorsement of suicidal thoughts, an automated alert system built into REDCap will notify the study team, including Risk Supervisors. Alerts of suicidality triggered by assessments collected through REDCap will automatically send a notification to ProtoCall Services, a 24/7 triage and crisis intervention service provided through contract. ProtoCall Services will initiate outreach with the participant to assess suicidality and provide urgent intervention if needed. Simultaneously, an automated alert will be sent to the DGC risk monitoring team. DGC's risk monitoring team will review the report provided by ProtoCall services and either conduct a follow-up with the participant if ProtoCall was unable to make contact in the first 24-72 hours, conduct a follow-up with the participant if the ProtoCall report indicates that a follow-up is expected, or sign off on the participant's record in the database that the report was reviewed and no follow-up was needed. Follow-up by a member of the DGC risk monitoring team will occur within one business day (Monday-Friday, 8am-5pm) if needed based on information provided by ProtoCall Services (e.g., in case of no contact). If information about the participant's current provider (e.g., OB/GYN) is on file, they may be additionally notified, if recommended by the Risk Supervisors.

In response to an endorsement of symptom worsening, this will be reviewed by the DGC risk monitoring team. See *Treatment changes* section related to response to elevated depression for participants.

In response to an endorsement of aggressive thoughts towards their infant when completing self-report assessments about mother-infant bonding, the DGC risk monitoring team will be notified. A member of the risk monitoring team will contact the participant to assess any risk. This will be reviewed by the Risk Supervisor.

The above events must be reviewed and verified by DGC Risk Supervisors. All actionable alerts will be fully documented, along with follow-up and outcome reporting. Any mandated reporting is conducted or supervised by DGC Risk Supervisors. If a response is not received from the clinical team, the clinical supervisor will be automatically notified.

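### The suicide-risk trigger differs between prescreening, the Risk Protocol and the quoted consent wording, the consent wording does not match who makes contact, and the no-contact follow-up time has no fixed limit or start

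*Protocol*

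**What the plan says.** Four places in the Protocol bear on this.

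- **Risk Protocol, opening paragraphs.** The scope is set by ideation: "The following protocol will be implemented in response to reports of suicidal ideation or worsening depression". A contracted crisis call center makes the initial outreach after remote surveys.
- **Risk Protocol, alert procedure.** The alert begins with thoughts alone: "In response to an endorsement of suicidal thoughts, an automated alert system built into REDCap will notify the study team". The outside crisis service is notified automatically and the study's risk monitoring team at the same time. The risk monitoring team then follows up in certain cases, one being "if ProtoCall was unable to make contact in the first 24-72 hours". The timing given is: "Follow-up by a member of the DGC risk monitoring team will occur within one business day", with business hours defined as Monday to Friday, 8am to 5pm, and no contact given as an example of when this applies.
- **Prescreening.** "Women who endorse suicidality with intent or means as part of online screening will receive follow-up for risk assessment", with the Risk Protocol named as the procedure to be followed.
- **Consent wording quoted at the end of the Risk Protocol.** The stated condition is: "If your responses to study surveys at any point indicate that you are feeling suicidal and with a plan to harm yourself". The clinical team is then notified and will contact the participant. The team also "may follow-up on potentially concerning responses to the symptom surveys". Sharing with anyone outside the research team is described for concern about imminent serious harm.

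**The concern.** The Prescreening section cites a procedure whose own entry condition is wider than the one it states. The Risk Protocol contains no intent-or-means threshold and no separate branch for screening, so the cross-reference does not match its target. The intent-or-means rule under Treatment Changes does not fill the gap, because it governs notice to treating clinicians and the offer of Tier 3 care, not the alert.

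The women affected are those with suicidal thoughts but no intent, means or plan. Staff following the alert procedure would act on their answer. Staff following the Prescreening section as written have no instruction to do so.

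The second issue is accurate consent. On the quoted wording, an enrolled woman who reports thoughts without a plan would not expect an automatic notice to an outside contractor, or that contractor's call.

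The third is that the no-contact case concerns women whom the crisis service has failed to reach, and the time allowed to the study team cannot be read from the text.

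**Working it through.** **Trigger and contact.** The passages side by side:

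| Place | Condition stated | Who acts |
|---|---|---|
| Risk Protocol, scope and alert procedure | Suicidal ideation or thoughts | Outside crisis service notified automatically and makes initial outreach; study team alerted at the same time |
| Prescreening | Suicidality with intent or means | Follow-up under the Risk Protocol |
| Consent wording | Feeling suicidal and having a plan; other concerning responses at discretion | Clinical team notified and makes contact |

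The three conditions are not the same. Intent or means is narrower than thoughts. A plan is a further, different qualifier. The consent wording also differs from the alert procedure on who makes contact, and on when information goes outside the research team (imminent harm in one, thoughts alone in the other).

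**Timing in the no-contact case.** The Protocol gives no overall figure to reproduce.

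Inputs from the Risk Protocol: a no-contact window W of 24 to 72 hours; a response time of one business day; business hours Monday to Friday, 8am to 5pm. Assumptions: one business day means 9 business hours (8am to 5pm), and there are no public holidays.

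*Reading A: the business day runs from the alert.* Elapsed time = time needed to accumulate 9 business hours from the alert.
- Shortest: alert at 8am on a weekday, due 5pm that day = 9 hours.
- Longest: alert Friday 5pm, due Monday 5pm = 3 × 24 = 72 hours.

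*Reading B: the business day runs from the end of the window.* Elapsed time = W + (9 to 72 hours).
- W = 24: 24 + 9 = 33 hours to 24 + 72 = 96 hours.
- W = 72: 72 + 9 = 81 hours to 72 + 72 = 144 hours. The maximum arises, for example, from an alert on Tuesday at 5pm: the window ends Friday 5pm and the business day ends Monday 5pm.

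A step through every quarter-hour alert time in a week gave the same ranges: 9 to 72, 33 to 96 and 81 to 144 hours. The latest permitted follow-up is therefore 72 or 144 hours, a factor of 144/72 = 2, depending on a starting point that the text does not give. Within Reading B alone, the open range moves the latest time from 96 to 144 hours.

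**The case against.** The strongest reply is that the main procedure is coherent. The scope sentence and the alert procedure agree that ideation starts it and that the contracted service calls first. On the trigger, that procedure is wider than the consent wording, so the mismatch leads to more follow-up, not less. The Prescreening section says what happens to women with intent or means; it does not say that others get nothing, and it concerns women not yet consented. All of this is fair. It means that the Prescreening wording bears on internal consistency and not on what an enrolled participant was told. It does not explain why a section citing the Risk Protocol states a different condition, and no intended difference for screening is declared.

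Several stronger readings are tempting but not supported:

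- *That the two times contradict each other.* One is the crisis service's contact window and the other is the study team's response, so they can run in sequence. The fault is an open range and an unstated start.
- *That a woman may be left unattended for six days.* The 144 hours is the extreme of Reading B. Meanwhile the 24/7 service is attempting contact, the study team has already been alerted, and escalation such as a wellness check is available.
- *That the consent wording excludes follow-up without a plan.* It makes it discretionary, and the Protocol says the form tells participants that staff monitor alerts from symptom surveys.
- *That REDCap can carry only one trigger.* Nothing in the Protocol says so; different surveys could have different rules.
- *That the consent form omits the crisis service.* Only excerpts are quoted, so this cannot be known.

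**Conclusion.** The point holds as an inconsistency in a safety procedure and in the consent wording quoted for it. Three different conditions are stated, and the Prescreening section points to a procedure that does not contain its condition. The quoted consent wording departs from the alert procedure on the trigger, on who makes contact, and on notice to a party outside the research team. The mismatch with what participants are told rests on those three items only; the quoted consent wording gives no time, so the timing issue adds nothing to it.

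The no-contact timing is a separate ambiguity: about 72 hours at the latest if counted from the alert, 96 hours after a 24-hour window, and 144 hours after a 72-hour window, with one business day taken as 9 business hours and no holidays.

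This is more than missing detail, because following one section or the other as written treats women with thoughts but no intent or means differently. It affects patient safety and the accuracy of consent, and changes no endpoint, sample size or analysis.

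**What to change.** 1. Reconcile the Prescreening section, the Risk Protocol's alert procedure and the quoted consent wording so that the trigger at screening and in follow-up surveys is stated consistently. If a difference is intended, state it.
2. Make the quoted consent wording agree with the procedure on the trigger, on who makes the initial contact, and on the automatic notice to the outside crisis service.
3. For the no-contact case, replace the range with one limit and state when the study team's clock starts.
4. Check the REDCap alert logic against the reconciled text.

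The clinical leads decide the threshold and the times; this review takes no position on either. The cost is a wording change to the Protocol and the consent form, and a check of the alert configuration.
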